2.3 Benefit/Risk Assessment

All patients who participate in this study will receive standard of care appropriate for their lung cancer as determined by their treating physician.

The technology to be used in this study is non-invasive and has been used previously in other settings, including clinical studies; it is believed to pose an extremely low risk to study patients. Patients using the wearable arm device have reported minor events of skin irritation and discomfort during sleeping. In addition, patients undergoing concomitant anti-coagulation therapy have experienced ecchymosis near the device site. As part of their standard of care, patients will undergo routine assessment by their physician, who will decide when regular visits should take place. Due to the nature of the technology used and the fact that all other procedures are standard of care, study-related or multiparametric mobile technology-related AEs are expected to be rare. The study sponsor, AstraZeneca (AZ), has concluded that this study has a favorable benefit/risk ratio.

Data from this pilot study will be used by AZ to decide whether a larger comparative study of patients with and without the technology is warranted, which will potentially benefit other patients in the future.

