8.3.2 Medical Device Deficiencies

Medical devices are being provided for use in this study as the study intervention. In order to fulfil regulatory reporting obligations worldwide, the Investigator is responsible for the detection and documentation of events meeting the definitions of device deficiency that occur during the study with such devices.

Definition of Device Deficiency

A device deficiency is any malfunction or deterioration in the characteristics and/or performance of a device as well as any inadequacy in the labelling or the instructions for use which, directly or indirectly, might lead to or might have led to the death of a participant/user/other person or to a serious deterioration in his/her state of health

NOTE: Incidents fulfilling the definition of an AE/SAE will also follow the processes outlined in [Section 8.3.1](#).

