2. ANALYSIS SETS

2.1 Definition of Analysis Sets

2.1.1 Safety Analysis Set

The Safety Analysis Set (SAF) will include all enrolled patients who take at least 1 dose of durvalumab.

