3. PRIMARY AND SECONDARY VARIABLES

3.1 Key Definitions

- The term ‘baseline’ is used to collectively refer to baseline visit or Day 1
 - Baseline visit is the date of informed consent.
 - This will apply to endpoints such as QoL, vital signs, spirometry, oximetry, etc.
 - For patient where there are multiple observations before the baseline visit, last non-missing observation will be used.
 - Day 1 is the date of first dose of Durvalumab. Day 1 can be up to 2 weeks after date of informed consent or may occur on the same date.
 - This will apply to endpoints related to pneumonitis, AEs, or durvalumab.
- Change from baseline will be calculated as follows:
 - Post-baseline value minus baseline value
 - If either the baseline value or post-baseline value is missing, the change from baseline is set to “missing”.
- The last dose date is defined as the last non-missing date where a non-zero dose of durvalumab is given/administered.
- The Study Day is the day relative to the Day 1. Study day will be calculated from date on or after date of Day 1 as follows:
Study day = date of assessment – date of first dose of durvalumab +1 if the date of assessment is on and after the date of first dose of durvalumab; Otherwise, Study day = date of assessment – date of first dose of durvalumab

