4.2.4.8 Adverse Events

An AE for drugs is the occurrence of an undesirable medical condition or the deterioration of a pre-existing medical condition following or during exposure to a pharmaceutical product or device, whether or not considered causally related to the product or device. An AE for medical devices is any untoward medical occurrence, unintended disease or injury, or any untoward clinical signs (including an abnormal laboratory finding) in patients, users, or other persons whether or not considered related to the medical device. This includes events considered related to the medical device and events considered related to the study procedures involved. AEs will be collected throughout the study, from informed consent until 30 days after the End-of-Study visit.

Treatment-emergent adverse events (TEAEs) are defined as any AEs that occur or worsen at any time after the start of administration of the first dose of durvalumab and through 30 days after the last dose of durvalumab. Treatment-emergent AEs will be characterized based on the onset date relative to each patient's first dose date. For adverse events with incomplete start dates, the imputed dates will be used to determine whether the adverse events are treatment emergent.

Adverse events will be summarized by the SOC and PT based on the MedDRA dictionary version 22.1 or later. The CTCAE grades will be summarized by SOC and PT, using the current version of National Cancer Institute (NCI) CTCAE. For summaries by SOC and PT, a patient will be counted once at the SOC level and once at each PT within the SOC level. For

summaries by SOC, PT, and CTCAE Grade, a patient will be counted once at the highest grade for which the event occurred at the SOC level and the highest grade for each unique PT within that SOC level. Therefore, patients may only contribute once to each PT and once to each SOC level. The summaries presenting frequency of AEs by SOC and PT will be ordered by overall descending frequency of SOC and then, within a SOC, by overall descending frequency of PT.

The following AE tables will be provided:

- TEAEs, overall and by SOC and PT
- TEAEs related to pneumonitis by maximum relationship, overall and by SOC and PT
- TEAEs related to medical devices by maximum relationship, overall SOC and PT

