With the exception of the overall summary AE table, only the TEAEs will be included in the summary tables; however, all AEs will be included in the listings. Any AE occurring before the first dose of durvalumab will be included in the data listings but will not be included in the summary tables of AEs.

Additional listings will be provided for deaths, AEs with an outcome of death, SAEs, AEs leading to discontinuation of durvalumab, study procedure and other significant AEs. TEAEs will be flagged in the listings. The death data will be listed in a separate listing.

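### The only device-related AE table opens at the first durvalumab dose, so a device reaction that starts earlier and does not worsen or recur appears only in listings and the tabulated rate can be too low

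*SAP*

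**What the plan says.** SAP 4.2.4.8 lists three AE tables. The one for the device is "TEAEs related to medical devices by maximum relationship, overall SOC and PT". It is a table of treatment-emergent events, and the section defines these as "any AEs that occur or worsen at any time after the start of administration of the first dose of durvalumab", up to 30 days after the last dose. The next sentence adds: "Treatment-emergent AEs will be characterized based on the onset date relative to each patient's first dose date". On earlier events the section says: "Any AE occurring before the first dose of durvalumab will be included in the data listings but will not be included in the summary tables".

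The population is set by SAP 4.2.4, which uses the SAF for safety analyses, and by SAP 2.1.1: "The Safety Analysis Set (SAF) will include all enrolled patients who take at least 1 dose of durvalumab".

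On timing, SAP 3.1 makes the Baseline visit the date of consent and Day 1 the date of the first dose: "Day 1 can be up to 2 weeks after date of informed consent or may occur on the same date". Protocol Table 1 places device training at Baseline. Protocol 8.2.1 requires only a signed consent form before onboarding. SAP 4.2.4.8 has AEs collected from consent until 30 days after the End-of-Study visit.

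**The concern.** The table measures the device, but its clock starts with the drug. Protocol 8.3.2 says: "Medical devices are being provided for use in this study as the study intervention". Protocol 8.3.2.1 times device deficiencies by device use, covering every period in which the device is in use. Device-related AEs get no matching window.

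The reactions the protocol expects come from wearing the device. Protocol 2.3 reports: "Patients using the wearable arm device have reported minor events of skin irritation and discomfort during sleeping". It adds bruising near the device site in patients on anticoagulants. Such reactions can begin as soon as wear begins, and for some patients that may be before the first infusion.

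Protocol 2.1 asks whether the devices fit into daily life with little burden. Protocol 4.2 makes patients' willingness and ability to wear them a critical factor in deciding on a larger trial. A device-related AE rate that leaves out part of the wear period would inform that judgement less well than the collected data allow.

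**Working it through.** **Step 1. What happens to each kind of event.** Take a dosed patient who uses the device before the first dose and has a device-related AE.

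| Course of the event | Device table | Listings |
|---|---|---|
| Starts and resolves before the first dose | No | Yes |
| Starts before, persists unchanged after | No | Yes |
| Starts before, worsens after | Yes by the definition, though the onset-date sentence leaves doubt | Yes |
| New episode after the first dose | Yes | Yes |

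The first two rows are the loss.

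**Step 2. Direction.** Let n be the number of dosed patients, k the number with any device-related AE from device start, and m the number whose only such events fall in the first two rows. The table shows (k − m)/n where the rate from device start is k/n. Since m ≥ 0, the window rule can lower the rate and cannot raise it. The restriction to dosed patients is separate and has no fixed direction: adding a never-dosed device user gives (k + 1)/(n + 1) if that patient reacted and k/(n + 1) if not.

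**Step 3. Length of the gap.** The first dose falls 0 to 14 days after Baseline (SAP 3.1; inclusion criterion 4). If onboarding is at Baseline, 0 to 14 days of possible device use per patient lie outside the window. The documents give no distribution of this gap.

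**Step 4. The plan's own precision figure.** Protocol Table 4 gives exact 95% Clopper-Pearson limits for n = 75. For 0 events the upper limit is 1 − 0.025^(1/75) = 4.8%, as printed. All 12 rows reproduce to 0.1 percentage point.

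**Step 5. Range under an assumption.** The documents give no device-AE rate and no onset times. Assume 8 of 75 patients react, and let s be the share whose reaction starts before the first dose and does not worsen or recur. The tabulated count is 8 × (1 − s).

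| s | Tabulated | Rate | Exact 95% CI |
|---|---|---|---|
| 0% | 8/75 | 10.7% | 4.7% to 19.9% |
| 25% | 6/75 | 8.0% | 3.0% to 16.6% |
| 50% | 4/75 | 5.3% | 1.5% to 13.1% |
| 75% | 2/75 | 2.7% | 0.3% to 9.3% |
| 100% | 0/75 | 0.0% | 0.0% to 4.8% |

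Each patient lost moves the rate by 1/75 = 1.3 percentage points. Both the 8 and s are assumptions.

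**The case against.** The strongest reply is that device use before the first dose is not established. No section states when home wear begins. SAP 4.2.4.7 schedules daily spirometry and oximetry from Day 1, which in the SAP is the first dose. Protocol Table 1 labels the Baseline visit Day 1, and SAP 3.1 allows consent and first dose on one date. If they coincide, nothing is lost. Against this, SAP 4.2.4.2 takes baseline oxygen saturation from the device system, and training and onboarding are tied to Baseline and consent, not to dosing. Earlier use is therefore possible and partly indicated, but its extent is unknown. This part of the objection stands and makes the point conditional.

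Three further replies also stand in part:

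- **Listings.** Pre-dose events stay in the listings with treatment-emergent events flagged, and in a descriptive study of 75 they can be read patient by patient. A listing does not give a rate, however.
- **Never-dosed patients.** Inclusion criterion 4 expects at least one dose, so these should be few.
- **Importance.** A device-related AE rate is not among the visible primary or secondary endpoints, and Protocol 4.2 does not name it as a success factor. Compliance is a closer visible measure of burden. The exploratory endpoints are redacted and cannot be judged.

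A reader might infer that the table counts only events that start after the first dose. The definition also admits events that worsen after it.

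**Conclusion.** The point holds in conditional form. As written, the SAP times its only device-related AE table from the first durvalumab dose. For patients who use the device before that dose, events that start earlier and do not worsen or recur are listed but not tabulated. The rate can be understated by this rule and cannot be overstated by it.

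The size cannot be fixed from the documents. It depends on when wear starts, on the gap to first dose and on onset times, none of which is given. Under the assumption of 8 reactions in 75 patients, the table could show anything from 10.7% down to 0.0%. The upper end applies when onboarding and first dose coincide.

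A reader might go further and conclude that two weeks of device exposure are lost for every patient, or that the rate is certain to be biased by a material amount. The documents do not support either: 14 days is the maximum gap, zero is expressly allowed, and no data on early reactions are given.

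**What to change.** In SAP 4.2.4.8:

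1. Build the device-related AE table from all device-related AEs recorded from informed consent, or from device onboarding if that date is captured, to the end of AE collection. Use all patients who received the device. The later closing point also keeps events in patients still in the study more than 30 days after their last dose.
2. Keep the durvalumab-anchored window and the SAF for the other AE tables.
3. Reconcile two neighbouring sentences. One exempts the overall summary AE table from the treatment-emergent limit; the other keeps pre-dose AEs out of the summary tables without exception. Neither puts pre-dose events in the device table.
4. State when home wear begins, and whether the onset-date sentence overrides worsening in classifying an event as treatment-emergent.

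The cost is SAP wording and one table with a different population and window, which needs a footnote. AEs are already collected from consent, so a window opening at consent needs no separate onboarding date, but patients who received the device must be identifiable. The device-related AE rate may look less favourable.

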5. INTERIM ANALYSES

No interim analyses are planned for this study.

6. CHANGES OF ANALYSIS FROM PROTOCOL

The primary analysis will be descriptive summary of occurrence of pneumonitis by grade. The primary analyses of logistic regression models used for identifying pneumonitis were changed and will be applied to exploratory endpoints which are not covered in this SAP.

CCI

Full analysis set specified in the protocol will not be used in the analysis covered in this SAP.

The analysis of change in QoL will only be applied to the pulmonary AE which has causal relation with durvalumab.

8. APPENDIX

8.1 General Changes

- Update SAP based on Protocol Amendment 5.0, 2 December 2020
- Updated Table of Contents in alignment with section revisions
- Changed from SYNH SAP template to AZ SAP template

8.2 List of pneumonitis terms

The following six terms are interchangeably used to identify pneumonitis in this study. They are drawn from a previous study of durvalumab treatment of NSCLC (N Engl J Med 2017; 377:1919-1929) and/or reviewed by study physician:

1. Pneumonitis
2. Radiation pneumonitis
3. Acute interstitial pneumonitis
4. Interstitial lung disease (ILD)
5. Pulmonary fibrosis

6. Immune-mediated pneumonitis

8.3 List of pulmonary event terms

The following list of terms are drawn from MedDRA (version 23.1) and defined by the AstraZeneca ILD Task Force as associated with identification/suspicion of ILD. These are used in this study as a wider class of pulmonary events:

1. Alveolar lung disease
2. Alveolar proteinosis
3. Alveolitis
4. Alveolitis allergic
5. Alveolitis necrotizing
6. Autoimmune lung disease
7. Bronchiolitis
8. Combined pulmonary fibrosis and emphysema
9. Diffuse alveolar damage
10. Eosinophilia myalgia syndrome
11. Eosinophilic granulomatosis with polyangiitis
12. Eosinophilic pneumonia
13. Eosinophilic pneumonia acute
14. Eosinophilic pneumonia chronic
15. Idiopathic interstitial pneumonia
16. Idiopathic pneumonia syndrome
17. Idiopathic pulmonary fibrosis
18. Lung infiltration
19. Necrotising bronchiolitis
20. Obliterative bronchiolitis
21. Progressive massive fibrosis
22. Pulmonary necrosis
23. Pulmonary radiation injury
24. Pulmonary toxicity
25. Pulmonary vasculitis
26. Radiation alveolitis
27. Radiation fibrosis – lung
28. Small airways disease
29. Transfusion-related acute lung injury
30. Acute respiratory distress syndrome
31. Allergic eosinophilia
32. Granulomatous pneumonitis
33. Organising pneumonia
34. Pulmonary sarcoidosis
35. Restrictive pulmonary disease
36. Rheumatoid lung

37. Sarcoidosis

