3.1 Study Objectives

The primary objective of the study is to describe the identification of treatment-emergent pneumonitis by grade (regardless of radiation therapy and/or immune-related etiology) in patients with unresectable Stage III NSCLC receiving durvalumab through the use of mobile technology which collects patient reported outcomes (PROs), vital signs (temperature, heart rate, respiratory rate), oxygen saturation (pulse oximetry), pulmonary function tests (spirometry), and physical movement (number of steps per day).

The secondary objectives are:

- To describe durvalumab treatment discontinuation due to pulmonary AEs, including pneumonitis
- To describe the duration of durvalumab use
- To describe the incidence of pulmonary AEs by grade
- To describe the severity of pulmonary AEs (including pneumonitis) and use of medication to manage AEs
- To describe the time to development of Grade 3 to 5 AEs, including pneumonitis
- To describe health-related quality of life (QoL) during the study and its relationship with AEs

The exploratory objectives are:

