3.2 Study Endpoints

The endpoint used to address the primary objective is:

- Occurrence of pneumonitis (either radiation or immune-mediated, by grade).
 - Grade of pneumonitis at diagnosis and highest grade of pneumonitis

The endpoints used to address the secondary objectives are:

- Occurrence of pulmonary AEs, including diagnoses of events, by grade
- Duration (days) of pulmonary AEs by type and grade
- Permanent discontinuation of durvalumab due to pulmonary AEs, including pneumonitis
- Early discontinuation of durvalumab treatment for any reason
- Duration (days) of durvalumab treatment
- Treatment interruptions, duration (days) of interruptions, and the reason for interruptions that will be captured in a standard data management form with the site physician documenting reasons in patient charts
- Time (days) to development of Grade 3 to 5 AEs, including pneumonitis

- Prescription of medication used to manage pulmonary AEs and duration (days) of treatment
- Change in QoL scores from baseline

The endpoints used to address the exploratory objectives are:

CCI

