4.2.2 Secondary Endpoints and Analyses

4.2.2.1 Occurrence of pulmonary AEs, including diagnoses of events, by grade

Definition of pulmonary AE:

- Pulmonary AE is defined as pulmonary adverse event recorded in the CRF. For this study, pulmonary AE do not include pneumonitis event. An AE episode start from onset date of an AE record and stop at the date when AE is resolved. List of terms for pulmonary event can be found in section 8.3.
- Pulmonary AE at diagnosis is defined as the earliest onset of pulmonary AE on or after Day 1, or onset of subsequent AE episode after previously resolved pulmonary AE.
- Highest CTCAE grade of pulmonary AE is defined as the pulmonary AE with the highest CTCAE grade from on or after Day 1 per AE episode. Pulmonary AE with the highest grade can occur on the same date or after the earliest pulmonary AE.
- Patient with response “yes” to CRF question “Is this baseline condition suggestive of a respiratory disease?” and the condition is on-going will not be included in this analysis.

Where there are only limited number of pulmonary AE, listing will be provided including relevant dates, CTCAE grade, and duration, etc.

Where there are sufficient number of pulmonary AE, frequency and percentage (95%CI) of patients with pulmonary AE will be summarized by CTCAE grade for pulmonary AE at diagnosis, and highest CTCAE grade of pulmonary AE and by relationship with pneumonitis.

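### The SAP narrows two secondary endpoints: pulmonary AEs to a list of 37 ILD-suspicion terms, and Grade 3 to 5 AEs to pneumonitis plus that list

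*SAP*

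**What the plan says.** **Protocol.** Section 3.2 lists "Occurrence of pulmonary AEs, including diagnoses of events, by grade" and "Time (days) to development of Grade 3 to 5 AEs, including pneumonitis" among the secondary endpoints, and also the duration of pulmonary AEs. Neither 3.1 nor 3.2 gives a term list or restricts the class to interstitial lung disease (ILD). Section 8.3.1 gives the study's focus as pneumonitis together with other pulmonary events. Section 8.3.1.4 has every AE collected, whatever its cause.

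**SAP.** Section 4.2.2.1 defines a pulmonary AE as one recorded in the CRF, then adds two statements: "For this study, pulmonary AE do not include pneumonitis event" and "List of terms for pulmonary event can be found in section 8.3". Section 8.3 holds 37 terms, drawn from MedDRA and described as "associated with identification/suspicion of ILD. These are used in this study as a wider class of pulmonary events". Section 8.2 holds the pneumonitis terms: "The following six terms are interchangeably used to identify pneumonitis in this study". Section 4.2.2.2 (duration) and section 4.2.2.7 (time to Grade 3-5) both refer back to the 4.2.2.1 definition, and each also has a pneumonitis analysis. SAP Table 1 names the time outcome as onset of Grade 3 to 5 AEs, without restricting it to the lung.

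**The concern.** The protocol endpoint is a general one, and the SAP fills it with terms chosen because they raise suspicion of one kind of lung disease. A reader of the report would take a rate headed pulmonary AEs to cover lung events at large. If the plan is followed as written, it covers ILD-type events only. Protocol 4.2 says that findings on the secondary endpoints will feed the decision on a larger trial, so the label matters.

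The Grade 3-5 endpoint has a second and independent mismatch. If it means all AEs, 4.2.2.7 drops every non-pulmonary Grade 3-5 event. If it means pulmonary AEs, the result depends on list 8.3.

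**Working it through.** **1. What the lists contain.** The numbered terms were counted and compared.
- List 8.2 has 6 terms and list 8.3 has 37. No term is on both.
- The word pneumonia occurs in 8.3 only in six qualified terms: three eosinophilic forms, idiopathic interstitial pneumonia, idiopathic pneumonia syndrome and organising pneumonia. Plain pneumonia is on neither list.
- Pleural effusion, pulmonary embolism, respiratory failure, bronchitis and pneumothorax are on neither list.

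**2. Where an unlisted lung event would appear.**

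| Result | Source of terms | Unlisted lung event included? |
|---|---|---|
| Pneumonitis occurrence (4.2.1) | 8.2 | No |
| Pulmonary AE occurrence with CI (4.2.2.1) | 8.3 | No |
| Duration (4.2.2.2) | 8.3, repeated for 8.2 | No |
| Time to Grade 3-5 (4.2.2.7) | 8.2, repeated for 8.3 | No |
| Treatment discontinuation (4.2.2.3 and 4.2.2.4, through disposition) | no term list named | Yes, as far as stated |
| Medication (4.2.2.8, through 4.2.4.5) | no term list named | Yes, as far as stated |
| TEAE summaries by SOC and PT, with CTCAE grade, and AE listings (4.2.4.8) | all terms | Yes |

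The TEAE tables count a patient once per SOC and once per PT. They therefore give no count pooled across SOCs, no duration and no time to event.

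**3. The plan's own precision figures.** Protocol Table 4 gives exact Clopper-Pearson limits for x patients with an event among n = 75. The lower limit is the 2.5% quantile of Beta(x, n − x + 1), and the upper limit is the 97.5% quantile of Beta(x + 1, n − x). All 12 rows reproduce. For example, x = 6 gives 8.0% (3.0% to 16.6%).

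**4. Effect per patient.** One patient whose only lung event is unlisted lowers the proportion, relative to a count of all pulmonary AEs, by 1/75 = 1.3 points. SAP 4.2.2.1 leaves out patients with an ongoing respiratory condition at baseline, so the denominator may be smaller. If that removed 20% (assumption), n = 60 and the effect is 1/60 = 1.7 points.

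**5. Illustration with assumed counts.** Suppose 6 of 75 patients have a listed event and this is enough for a percentage to be reported.

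| Patients with only an unlisted event (assumed) | Patients with any pulmonary AE | Proportion (exact 95% CI) |
|---|---|---|
| 0 | 6 | 8.0% (3.0% to 16.6%) |
| 1 | 7 | 9.3% (3.8% to 18.3%) |
| 3 | 9 | 12.0% (5.6% to 21.6%) |
| 5 | 11 | 14.7% (7.6% to 24.7%) |

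The SAP would show the first row in every case.

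**6. What the documents offer on size.** The one pneumonia figure is in protocol 2.2: 1.1% of durvalumab patients in the cited Phase 3 trial stopped treatment because of it. Carried over to this study (assumption), that is 0.011 × 75 = 0.8 patients, with a chance of at least one of 1 − (1 − 0.011)^75 = 56%. It is a discontinuation rate in another trial, not an incidence, so it cannot size the gap.

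**The case against.** The strongest case is that this is a choice and not a contradiction. The protocol gives no term list, so the SAP had to supply one. It did so openly, naming the source and stating that pneumonitis is excluded. Which terms belong is partly a medical judgement. All the analyses are descriptive, and the primary endpoint is untouched. Unlisted events keep their grade summaries by SOC and PT and their place in the listings, which goes a good way towards occurrence by grade. Much of this stands. It limits the loss to the pooled proportion with its interval, the duration and the time to Grade 3-5. It does not explain why a class chosen for ILD suspicion carries the general label.

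The definition also says recorded in the CRF, and the CRF is not available. It might carry a wider pulmonary flag. That leaves some ambiguity, but the SAP names 8.3 as the place for the terms.

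Four stronger readings are tempting, and the documents do not support them.
- *Leaving pneumonitis out of the class is an error.* It is not. Pneumonitis gets the same three analyses separately. The objective "To describe the severity of pulmonary AEs (including pneumonitis) and use of medication to manage AEs" concerns severity and medication, and does not require a pooled occurrence row.
- *The protocol's data collection table places pneumonia in the endpoint.* It does not. The row that names pneumonia asks for details on pneumonitis.
- *The narrowing is undisclosed.* This cannot be said, because SAP section 6 (changes from protocol) is partly redacted.
- *The reported proportion will be biased.* Not always. The SAP says "Where there are only limited number of pulmonary AE, listing will be provided including relevant dates, CTCAE grade, and duration, etc". In that case no percentage is produced, and the unlisted events are simply absent from that listing.

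**Conclusion.** The point holds and should be fixed. Followed as written, the plan gives a pulmonary AE result narrower than the protocol endpoint, for occurrence, duration and time to Grade 3-5 alike. Section 4.2.2.7 is also narrower than both the protocol endpoint and SAP Table 1. This second mismatch does not depend on how list 8.3 is read.

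The size is unknown, because the documents give no incidence of lung events outside the lists. The only firm figure is 1.3 points per affected patient, and it assumes that 75 patients are analysed. The counts in the illustration are assumptions, not forecasts. The conclusion on the first part rests on reading 8.3 as the definition of the class. If 8.3 is not meant to be exhaustive, the SAP must say what else counts, since two programmers could otherwise produce different endpoints.

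**What to change.** 1. Before database lock, add to the SAP appendix a list of other pulmonary AE terms selected by the study physician, with at least pneumonia and other lower-respiratory infections on it. Label the 8.3 class ILD-type.
2. Report occurrence, duration and time to Grade 3-5 for all pulmonary AEs, meaning 8.3 plus the added terms, beside the existing 8.3 and pneumonitis results. Where events are few, give the listing for the same groups. A total that includes pneumonitis is optional.
3. In 4.2.2.7, add time to first Grade 3-5 AE of any kind. If the endpoint is meant to be pulmonary only, correct SAP Table 1 and record the restriction in section 6, unless it is already there under redaction.

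The cost is SAP text, an appendix list and a little more programming. The AEs are already collected and are to be MedDRA-coded. The drawback is a more mixed category, in which symptoms of one pneumonitis episode may be counted again. A selected term list, rather than a whole SOC, limits this, and the separate 8.3 and pneumonitis results remain interpretable.
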